prescribed in NSABP B-39/RTOG 0413 as well as the Canadian Accelerated Partial Breast Irradiation Using Three-Dimensional Conformal External Beam Radiation Therapy (RAPID) randomized trials. Olivotto et al. recently reported the interim cosmetic and toxicity results from the latter study which compared 3D-conformal APBI to whole breast irradiation (WBI). 82% of patients in the WBI arm received 42.5Gy in 16 fractions, and just 21% of patients received a boost. At 3 years, 29% of patients in the APBI arm had fair or poor cosmesis compared to 19% at baseline, an absolute difference of 10%. In the WBI arm, the rate of fair or poor cosmesis at 3 years was 17%, the same rate as at baseline. Telangiectasia and breast induration were also significantly more common with external beam APBI ($p<0.001$), as was fat necrosis ($p=0.01$).⁴⁷ Other institutions have also noted adverse toxicity with similar regimens.^{22,48}

There are likely several reasons for the higher than expected adverse cosmesis seen in the RAPID trial that may be also relevant to the increased complications seen with brachytherapy in population based analyses. These considerations have been taken into account in the development of the brachytherapy, external beam photon and proton fractionation regimens of this study. First, the dose of 38.5Gy in 10 fractions given twice daily was too high. The RAPID trial investigators recognized that this prescription had a higher biologic equivalence than the whole breast regimens used in the study, but they hypothesized that the reduced volume of APBI would make up for this difference. Indeed, using an α/β ratio of 3.5 for late effects, the 3.85Gy x 10 fraction regimen translates into 51.5Gy in 2 Gy fractions, higher than the 2Gy fraction equivalent dose of 42.5Gy delivered in 16 fractions (47.7Gy₂) which was received by the majority of patients in the WBI control arm of the study.

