3.46 Extensive intraductal component

3.47 Active connective tissue disease

3.48 Reduction mammoplasty if 3DCRT or proton APBI are planned

3.49 Last surgery >10 weeks from enrollment

4.0 Test Schedule

Assessments, tests and procedures	Active Monitoring Phase				Observation
	Baseline ²	Radiation Treatment	Last day of radiation treatment (+/-2 days)	12 weeks (+/- 8 weeks) post-radiation	
History and Physical exam (including breast assessment/exam) ¹	X		X	X	X
Mammogram	X ¹¹				X ⁸
Consent	X				
Cosmetic and QOL Outcome Assessment (see section 11.3 and Appendix)	X		X	X	X
Digital Photograph	X ¹⁰		X	X	X
Histologic Assessment	X ³				
Radiation toxicity assessment (see section 10.4)	X		X	X	X
Serum pregnancy test	X ⁴				
Blood specimen ^{5,R}	X ¹²		X		
Clinically indicated treatment		X			

Surgical tumor specimen ^{6,R}	X ⁹				
----------------------------------------	----------------	--	--	--	--

1. A general clinical history & physical must be done \leq 8 weeks prior to registration. This should include assessment of ECOG performance status (see Appendix I).
2. Procedures done prior to radiation therapy.
3. Outside pathology must be reviewed at the treating institution.
4. For women of childbearing potential only
5. See section 14 for collection time and preparation of samples
6. See section 17 for collection time and preparation of samples
7. Patients that cannot come back to Mayo Rochester within the time constraints of the follow-up schedule; efforts to obtain outside records and send QOL's to be completed will occur however the specifics of the test schedule may not be captured. Observation will occur for a total of 5 years unless the patient goes off study.
8. As clinically indicated
9. Collect post-surgery
10. Ideally prior to surgery but can be done prior to radiation
11. Completed \leq 6 months prior to study entry
12. Radiation Oncology Registry and Biobank (IRB: 15-000136): Blood specimen is required to be collected prior to the start of radiation therapy.
- R. Research required testing

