16.0 Statistical Considerations and Methodology

- 16.1 Overview: This is a single arm phase II study evaluating the rate of adverse cosmesis (defined as fair or poor cosmesis) at 3 years, compared to baseline, of 3 fraction accelerated APBI. For the analysis of the primary endpoint, patients will be pooled across the three treatment techniques (photon, proton, and brachytherapy) as was done in the the NSABP B-39/RTOG 0413 national multi-institutional randomized control trial comparing APBI with WBI. The three techniques utilized are recognized as standard options for the delivery of APBI, and there is no evidence that any technique is superior to any other with commonly used dose and fractionation regimens.⁴ The primary endpoint is the difference from baseline in the percentage of patients with adverse cosmesis (fair or poor cosmesis) at 3 years. The intent is to determine whether the difference of adverse cosmesis rate is acceptable. Of interest is whether the 3 fraction accelerated APBI results in an unacceptable increase in the adverse cosmesis rate at the end of 3 years, compared to baseline. If it does not, then the 3 fraction accelerated APBI will be recommended for further study. If the change in adverse cosmesis rate is found to be unacceptable, then the recommendation would be to do no further studies of the 3 fraction accelerated APBI. In addition to adverse cosmesis, this study will assess many additional secondary endpoints including IBTR (both invasive and non-invasive IBTRs will be considered), acute and late toxicity profile, quality of life measures, and translational studies.

16.2 **Primary Endpoint:** The primary endpoint is the percentage difference in patients with adverse cosmesis (fair or poor cosmesis) at 3 years compared to baseline. Cosmesis will be assessed by a trained nurse provider using the Harvard Cosmesis Scale.

All patients meeting the eligibility criteria who have signed a consent form, and begun treatment will be considered evaluable for the primary endpoint.

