16.4 Study Sample Size, Decision Rule, and Study Duration

16.41 *Sample size:* This study requires 153 evaluable women for the primary endpoint analysis. We anticipate accruing 15 additional patients to account for ineligibility, cancellation, major treatment violation, or other reasons. The maximum projected accrual is therefore 168 women, and we expect a maximum of 60 and a minimum of 40 women within each cohort (photon, proton, and brachytherapy).

16.42 *Study Decision Rule and Operating Characteristics:* Olivotto et al. previously reported interim cosmetic and toxicity results from a randomized trial comparing APBI using 3D-CRT versus WBI. In this study, the same 3DCRT dose and fractionation was used as in the previously discussed NSABP B-39/RTOG 0413 randomized controlled trial comparing 3DCRT or brachytherapy APBI with WBI. At 3 years, the percentage difference in patients with adverse cosmesis in the APBI arm compared to baseline by trained nursing assessment was 10.6%. The proposed analysis is to compute the percentage difference in patients with adverse cosmesis (fair or poor cosmesis) at 3 years compared to baseline. A one-sided 95% confidence interval (with the upper bound of the interval) was computed, by assuming the difference in adverse cosmesis rate at 3 years compared to baseline is 10%, and the distance from 10% to the upper bound of the CI is 4%. The decision rule would be of the following:

- If the upper bound of the one-sided CI for the difference of adverse cosmesis rate lies above 14%, then recommend no further investigation and conclude that there is no sufficient evidence to accept the adverse cosmesis rate of 3 fraction accelerated APBI.
- If the upper bound of the one-sided CI for the difference of adverse cosmesis rate lies below 14%, then recommend further investigation and conclude the increase in 3-year adverse cosmesis rate of 3 fraction accelerated APBI is potentially acceptable.

The study operating characteristics is determined as the chance of declaring that APBI warrants further study, assuming a true value for the difference in adverse cosmesis rate at 3 years compared to baseline for APBI. The table below shows the operating characteristics of this trial with 153 patients and the decision rule given above.

True increase in adverse cosmesis rate at 3 years compared to baseline	Probability of concluding PBI warrants further study
5%	98.4%
10%	72.8%
15%	48.6%
20%	29.8%

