16.44 Accrual time and Study duration: Since 10/1/2012 patients have been treated with brachytherapy APBI using an 8 or 10 fraction regimen and prospectively followed as part of a clinical registry at the Mayo Clinic in Rochester, MN. Patient interest in the procedure has steadily increased, and in the last 3 months, 13 patients have been treated (median 4.3 patients per month), all of whom would be eligible for this study. A similar to increased level of accrual of brachytherapy patients is anticipated during the course of this study as familiarity with this procedure amongst surgical and radiation oncology providers rises. With the addition of the photon APBI alternative for patients, we anticipate an accrual rate of 5 patients per month for the first year until the opening of

the Mayo proton facility, after which an accrual of 8 patients per month is anticipated. Therefore, the accrual period for this study is expected to be approximately 3 years. We plan to open this study at the Mayo Clinic in Scottsdale and Jacksonville which will further enhance accrual. Final analysis may begin approximately 5 years after the trial begins, i.e. as soon as the last patient registered has been observed for at least 24 months. A maximum of 60 patients and a minimum of 40 patients will be enrolled per treatment arm.

16.5 **Primary Analysis:** The primary analysis will be to estimate the percentage difference in patients with adverse cosmesis (fair or poor cosmesis) at 3 years compared to baseline. All patients meeting the eligibility criteria who have signed a consent form and started treatment will be in the primary analysis. The percentage difference in patients with adverse cosmesis will be estimated using a binomial estimator (number of women who had an adverse cosmesis event at 3 years minus number of women who had an adverse cosmesis event at baseline, and then divided by total number of women in the primary analysis) and a 95% exact binomial confidence interval. As mentioned above, the following decisions will be made based on the 95% CI:

- ***The upper bound of the 95% CI lies below 14%:*** APBI adverse cosmesis is acceptable.
- ***The upper bound of the 95% CI lies above 14%:*** No evidence to show that APBI adverse cosmesis is acceptable.

16.6 **Secondary Analyses**

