16.61 *Acute adverse events (up to 90 days post-RT):* All patients who were registered to the study and started treatment will be included in the acute adverse event analysis. An acute adverse event is an AE, regardless of attribution, that occurs up to 90 days post-RT. The maximum grade for each type of acute AE will be recorded for each patient. Data will be summarized as frequencies and relative frequencies. Additionally, the relationship of the adverse event(s) to the study treatment will be taken into consideration.

16.62 *Late adverse events:* All patients who were registered to the study and started treatment will be included in the late adverse event analysis. A late adverse event is an AE, regardless of attribution, that occurs at least 90 days post-RT and up to 3 years post-RT. The maximum grade for each type of late AE will be recorded for each patient. Data will be summarized as frequencies and relative frequencies. Additionally, the relationship of the adverse event(s) to the study treatment will be taken into consideration. Prior APBI reports have suggested rates of grade 3 or 4 toxicity to be $\leq 10\%$.^{18,47,55,56}

16.63 *Quality of life:* The QOL measurements will be summarized at each time point as mean \pm SD and median (minimum value, maximum value). Changes in the QOL measurements from baseline will be determined at each follow-up measurement. These will be displayed as spaghetti plots. The assessment of the changes at each time point will be done with a paired t-test or Wilcoxon signed rank test, whichever is appropriate.

16.64 *Cosmesis*: The values of the cosmesis instruments (patient self-reported and panel-assessed) will be summarized with the frequencies of fair or poor cosmesis events at baseline and 3 years, and the difference at 3 years, as well as their relative exact binomial confidence intervals.

16.65 *IBTR incidence*: The IBTR cumulative incidence will be estimated using a competing risks method (Gooley et al.). The competing risks will be regional/distant breast cancer recurrence and death.

16.66 *Regional recurrence incidence*: The regional breast cancer recurrence cumulative incidence will be estimated using a competing risks method (Gooley et al.). The competing risks will be local/distant breast cancer recurrence and death.

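### Section 16.5 puts a one-sample exact binomial interval on a paired net change, so the 14% decision bound is too low whenever some women improve

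*Combined protocol and SAP*

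**What the plan says.** Section 16.5 takes as its estimate "number of women who had an adverse cosmesis event at 3 years minus number of women who had an adverse cosmesis event at baseline", divided by the number of women in the primary analysis. It attaches an exact binomial interval at the 95% level and compares the upper limit with 14%. It does not say whether the interval is one- or two-sided, but it refers back to the decision rule of 16.42, which is one-sided: "If the upper bound of the one-sided CI for the difference of adverse cosmesis rate lies below 14" percent, further investigation is recommended.

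The sample size in 16.41 and 16.42 has the same basis. An increase of 10% is assumed, and "the distance from 10% to the upper bound of the CI is 4" percentage points. The result is stated as "This study requires 153 evaluable women for the primary endpoint analysis".

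Section 16.64 carries the interval over to the patient-reported and panel scores, for the two single proportions "and the difference at 3 years, as well as their relative exact binomial confidence intervals".

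No section gives a paired method for cosmesis. Section 16.63 does use paired tests for quality of life.

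**The concern.** Each woman is scored at baseline and again at 3 years. Women who are adverse at both times cancel in the subtraction, which leaves those who worsened minus those who improved. This net count can go down as well as up, and can be negative, where an exact binomial interval is undefined. It has the binomial variance only if improvement never happens.

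The plan does not rule improvement out. No eligibility criterion excludes women with fair or poor cosmesis at baseline. In the benchmark trial described in 1.3.2, "29% of patients in the APBI arm had fair or poor cosmesis compared to 19% at baseline". Subtracting a baseline count makes sense only if some women start adverse.

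Provided the pooling conditions of 16.43 are met, this one bound decides whether the regimen goes forward. The error is towards accepting a regimen whose cosmetic harm is at the plan's own limit.

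**Working it through.** **Inputs.** n = 153 (16.41); limit 14% and one-sided 95% bound (16.42); planning increase 10% with 4 points to the bound (16.42); estimator and exact binomial interval (16.5). Let d be the true net increase and q the proportion of women who improve. The documents do not give q, so 0 to 4% is assumed.

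**Reproducing the sample size.** The one-sample Wald formula gives 1.645² × 0.10 × 0.90 / 0.04² = 152.2, rounded up to 153. The design therefore also assumes no improvers.

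**Variance.** Per woman, the change is +1 with probability d + q, −1 with probability q, and 0 otherwise. Its variance is (d + 2q) − d² = d(1 − d) + 2q. The binomial interval leaves out 2q.

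**Cut-offs with n = 153.** Exact one-sided 95% upper bounds are 13.93% at a net count of 14 and 14.69% at 15, so the rule accepts at 14 or fewer. Exact two-sided 95% upper limits are 13.30% at 12 and 14.09% at 13, so on that reading it accepts at 12 or fewer.

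**False acceptance at a true 14% increase.** This is P(worsened − improved ≤ cut-off), from the exact trinomial with probabilities 0.14 + q, q and 0.86 − 2q:

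| Improving (assumed) | One-sided exact | Two-sided exact | One-sided Tango |
|---|---|---|---|
| 0% | 4.8% | 1.4% | 4.8% |
| 0.5% | 5.6% | 1.9% | 4.9% |
| 1% | 6.4% | 2.3% | 4.7% |
| 2% | 7.9% | 3.3% | 4.8% |
| 4% | 10.4% | 5.2% | 4.9% |

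The nominal levels are 5% one-sided and 2.5% two-sided. They are passed at about 0.13% and 1.2% improving, respectively.

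**Scale of the assumption.** If 19% were adverse at baseline, as in the benchmark arm, then 1, 2 and 4% improving means that 1/19, 2/19 and 4/19 of those women recover: 5, 11 and 21%.

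**Single decisions.** At a net count of 14 the plan's bound is 13.93% and the regimen is accepted, whatever the number of improvers. With two improvers the one-sided Tango bound is 14.12%; with four, the paired Wald bound is 14.04%. At a net count of 13, six improvers are needed for Tango to exceed the limit (14.12%).

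**Precision.** The 4 points are a Wald figure. At 15/153 (9.8%) the exact bound is 14.69%, already 4.9 points above the estimate with nobody improving. The Tango distance is 4.7, 5.1, 5.3 and 5.8 points with 0, 2, 3 and 6 improvers. To keep 4 points on the paired Wald variance, n = 1.645² × (0.09 + 2q) / 0.04², which is about 187, 220 and 288 for q = 1, 2 and 4%.

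**The case against.** The strongest objection is that the size of the error rests wholly on q. The 19% comes from another trial; it shows that women can start adverse, not that they recover. Baseline in this trial may precede surgery. Section 4.0 requires baseline procedures only before radiation, but says of the baseline photographs: "Ideally prior to surgery but can be done prior to radiation". Under 7.12, brachytherapy patients (40 to 60 women) are seen preoperatively, so an early baseline is plausible for them. If the nurse's score follows the photographs, which the documents do not say, few women could improve and the binomial rule would be nearly correct. This stands, and it is why the figures are given as a range.

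Second, the larger figures need the one-sided reading. On the two-sided reading the error is at most 3.3% up to 2% improving. This also stands, though the back-reference in 16.5 favours one-sided.

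Third, exact intervals are conservative, so the error at 14% does not exceed nominal the moment one woman improves. That slack comes from the discreteness of the counts. It does not restore the coverage guarantee, and one-sided it is gone at 0.13% improving.

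Fourth, this is a phase II recommendation, and at a true 20% increase the one-sided exact rule still accepts in only 0.1 to 0.4% of trials with 1 to 4% improving. That is so; the excess error matters near the limit, where the rule has to discriminate.

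**Conclusion.** The concern holds. The interval in 16.5 does not fit the estimator it is attached to, and no other section repairs this. The mismatch follows from the definition of the estimate; how much it matters depends on an improvement rate the documents do not give. On the one-sided reading, false acceptance at the 14% limit rises from 4.8% with no improvers to 6.4, 7.9 and 10.4% at an assumed 1, 2 and 4%. On the two-sided reading it rises from 1.4% to 2.3, 3.3 and 5.2%, against 2.5%. If baseline is scored before surgery, the true figure may lie near the bottom of these ranges. Because this bound is the formal criterion for the primary conclusion, it should be corrected before the analysis.

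**What to change.** **16.5.** Replace the exact binomial interval with a one-sided 95% upper confidence bound for the difference of paired proportions, by the Tango score method, from the 2×2 table of baseline by 3-year adverse cosmesis. Keep the 14% limit. If two-sided was meant, say so and use the two-sided 95% Tango interval (error 2.7, 2.2, 2.2 and 2.2% at 0, 1, 2 and 4% improving).

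State which women enter the table. It needs both scores, whereas 16.2 counts every eligible, consented woman who has "begun treatment will be considered evaluable for the primary endpoint". One option is to use women with both scores and report how many lack the 3-year score. If fewer than 153 remain, the cut-offs and probabilities given here change.

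**16.64.** Change only the interval for the difference; exact intervals for the single proportions are valid.

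**16.42.** Keep n = 153, describe the 4 points as a Wald planning figure without improvers, and restate the operating characteristics. The one-sided Tango rule with 153 women accepts:

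| True increase | 0% improving | 1% | 2% | 4% |
|---|---|---|---|---|
| 5% | 99.0% | 97.6% | 95.3% | 89.7% |
| 10% | 42.8% | 38.6% | 35.3% | 30.9% |
| 15% | 2.3% | 2.4% | 2.5% | 2.7% |
| 20% | <0.1% | <0.1% | <0.1% | <0.1% |

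The gap from the printed 72.8, 48.6 and 29.8% at 10, 15 and 20% is not mainly due to pairing. The one-sided exact rule with no improvers gives 42.8, 2.3 and 0.02%, so that table needs separate correction.

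**Cost.** The change is SAP wording and a different procedure on scores already planned. On the one-sided reading nothing is lost if nobody improves: both rules accept 99.0, 42.8 and 4.8% at true increases of 5, 10 and 14%. With 1, 2 and 4% improving, Tango accepts 97.6, 95.3 and 89.7% at a true 5% increase, against 97.9, 96.7 and 93.9% under the exact rule. At a true 10% increase it accepts 38.6, 35.3 and 30.9%, against 43.2, 43.5 and 44.1%. No patients are added only because the 4-point precision is given up. If 16.5 was meant as two-sided, the one-sided paired bound would be more lenient when few improve: 4.8, 4.7 and 4.8% against 1.4, 2.3 and 3.3% at 0, 1 and 2% improving. The sidedness must therefore be settled first.

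### Section 16.5 does not say that its 95% exact interval is one-sided, as 16.42 requires; read as two-sided, the go cut-off falls from 14 to 12 net events of 153

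*Combined protocol and SAP*

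**What the plan says.** Section 16.42 is explicit about the interval behind the decision: "A one-sided 95% confidence interval (with the upper bound of the interval) was computed". It sets the planning values in the same sentence: "by assuming the difference in adverse cosmesis rate at 3 years compared to baseline is 10" per cent, and "the distance from 10% to the upper bound of the CI is 4" per cent. Both of its decision bullets name the one-sided interval; the favourable one begins "If the upper bound of the one-sided CI for the difference of adverse cosmesis rate lies below 14" per cent. Section 16.41 gives the size: "This study requires 153 evaluable women for the primary endpoint analysis".

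Section 16.5 then defines the primary analysis. The estimate is the number of women with adverse cosmesis at 3 years minus the number at baseline, divided by all women analysed, with "a 95% exact binomial confidence interval". Its favourable bullet reads "The upper bound of the 95% CI lies below 14" per cent. Neither the estimator sentence nor either bullet says one-sided. The bullets are introduced by a phrase that refers back to what has already been stated, and 16.42 is the only earlier place where a 14% rule appears.

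**The concern.** A 95% exact binomial interval with no further qualification is normally produced as the two-sided Clopper-Pearson interval. Its upper limit is a one-sided 97.5% bound. An analyst who programs 16.5 by its conventional meaning would therefore apply a stricter rule than the one in 16.42, on which the trial was sized.

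Section 16.5 also names the exact method, which 16.42 does not. A reader cannot tell whether the missing qualifier is shorthand or a second deliberate change. The bound decides whether the regimen is recommended for further study, and in an open-label single-arm trial its sidedness should not be left to be settled once the data are visible.

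**Working it through.** **Inputs.** Assumed increase p = 0.10, distance to the upper bound d = 0.04 and threshold 14% (16.42); evaluable N = 153 (16.41); exact binomial interval on the net count (16.5).

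**1. Which sidedness gives 153?** The plan states no formula. The single-proportion normal-approximation formula is n = z² p(1 − p) / d².

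- One-sided 95%, z = 1.645: 2.706 × 0.09 / 0.0016 = 152.2, rounded up to **153**. This is the plan's figure.
- Two-sided 95%, z = 1.960: 3.842 × 0.09 / 0.0016 = 216.1, rounded up to **217**. This does not match.

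**2. Go cut-off with the exact interval.** Following 16.5, the net count x is treated as binomial with N = 153. The upper limit is the 1 − a quantile of a beta distribution with parameters x + 1 and N − x, where a = 0.05 (one-sided) or 0.025 (two-sided).

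| Net events | Observed | Upper limit, one-sided 95% | Upper limit, two-sided 95% | Decision |
|---|---|---|---|---|
| 12 | 7.84% | 12.40% | 13.30% | go under both |
| 13 | 8.50% | 13.17% | 14.09% | go / no-go |
| 14 | 9.15% | 13.93% | 14.88% | go / no-go |
| 15 | 9.80% | 14.69% | 15.65% | no-go under both |

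The largest net count that gives a go is 14 one-sided and 12 two-sided. The two readings disagree only at 13 and 14.

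**3. How often this matters.** The probability of a go is P(X ≤ 14) one-sided or P(X ≤ 12) two-sided, with X binomial (153, true increase). The difference is the chance of landing on 13 or 14.

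| True increase | Go, one-sided | Go, two-sided | Decision flips |
|---|---|---|---|
| 5% | 99.0% | 95.6% | 3.4% |
| 8% | 75.7% | 54.7% | 21.0% |
| 10% | 42.8% | 23.0% | 19.8% |
| 15% | 2.3% | 0.6% | 1.7% |

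**4. Can the plan's own table settle the intent?** The table in 16.42 gives go probabilities of 98.4%, 72.8%, 48.6% and 29.8% at true increases of 5%, 10%, 15% and 20%. The first three differ from both columns above. Exact, Wald and Wilson bounds, one-sided and two-sided, did not reproduce the table as a whole. Nor did paired and unpaired difference versions under assumed baseline and improvement rates. The table therefore cannot show which interval was meant.

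**The case against.** The best defence is that 16.5 only abbreviates 16.42. It refers back to the earlier rule, keeps the same 14% threshold and uses only the upper bound. It mentions no lower limit, and nowhere is the primary interval called two-sided; the two-sided statement in 16.7 belongs to the exploratory comparisons. The sizing supports the one-sided reading as well. All of this stands, and it shows which correction is right. It does not put the missing words into the text that will be programmed.

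A reader might infer that the two sections contradict each other outright, so that the same data generally give two answers. The documents do not support that. The conflict arises only if 16.5 is read as two-sided, and then only at two values of the net count.

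The two-sided reading also errs on the strict side. At a true increase of 14% the chance of a go is 4.8% one-sided and 1.4% two-sided, so both stay below 5%. The harm is a lost correct go, not a false acceptance.

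Finally, stating the sidedness does not fully align the sizing with the analysis. The normal-approximation bound that reproduces 153 gives 13.76% at 15 net events, a go; the exact one-sided bound gives 14.69%, a no-go. That is a difference of method, separate from sidedness.

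**Conclusion.** The point holds as an unresolved ambiguity in the primary decision rule, with a clear indication of what was meant. If 16.5 is programmed as a conventional two-sided interval, the chance of a go at the planning value of 10% falls from 42.8% to 23.0%, a little over half the one-sided figure.

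Two conditions apply. The figures follow 16.5 in treating a net paired difference as a binomial count, which is valid only if no woman moves from adverse cosmesis at baseline to acceptable cosmesis at 3 years. And because the published operating characteristics were not reproduced under either reading, the comparison measures the effect of sidedness under the method in 16.5; it does not measure a departure from the table in 16.42.

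**What to change.** In 16.5, specify a one-sided 95% upper confidence bound in the estimator sentence and in both decision bullets, so that the rule matches 16.42. If a two-sided 95% interval is also to be reported, label it descriptive and say that it plays no part in the decision. This costs wording only: the sample size, data collection and threshold are unchanged. It should be made before the primary analysis is run.
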